## **STUDY DEVICE**

Visions® PV.035 IVUS catheter (Volcano, San Diego, CA) [Appendix B]

## **STUDY PROCEDURES**

### SCREENING VISIT

Patients will be screened for the study using inclusion and exclusion criteria outlined in Section 3. Informed consent will be obtained as detailed in Section 0. The following data will be collected at screening once informed consent is obtained:

Demographics to Record:

1. Baseline characteristics:

- a. Age
- b. Gender
- c. Body mass index
- d. Height
- e. Race

2. Medical Co-morbidities

- a. Diabetes
- b. Creatinine clearance rate (ESRD)
- c. Hypertension
- d. Coronary artery disease
- e. Prior open chest surgery
- f. Left ventricular ejection fraction (%)
- g. NYHA functional class

3. Lead Data

- a. Reason for extraction (indication per HRS Consensus Guidelines)
- b. Type of leads
  - i. Location
  - ii. Fixation type
  - iii. Function
  - iv. SVC Coil (Y/N, single or dual)
- c. Number of leads
- d. Lead dwell times

4. Routine laboratory data including blood culture or wound culture results if applicable.

5. Chest x-ray findings

6. Transesophageal echocardiography (TEE) or transthoracic echocardiogram (if performed)

## PROCEDURE

Transvenous lead extraction (TLE) should be performed in an EP lab, cardiac OR or hybrid lab as is customary based on the operator's preference. A PA and lateral CXR is recommended any time prior to TLE to confirm the number, type and location of all implanted leads and hardware. The following tests are recommended but left to the discretion of the operator: (1) transesophageal echocardiography (TEE) or transthoracic echocardiogram to look for vegetations (thrombus w/ infection indication) and tricuspid valve (TV) regurgitation, and (2) right or left subclavian vein venogram to evaluate patency of venous structures. If performed, reports of these tests will be collected. Prior to the start of the procedure, the operator will need to perform the following assessment:

1. Assessment of risk and /or difficulty of extraction based on clinical variables alone
  - a. Based on the following clinical variables, what is your assessment of risk or difficulty of extraction? (LOW (L) = 1 point, MODERATE (M) = 2 points, HIGH (H) = 3 points)
 

i. Lead dwell time	LOW	MODERATE	HIGH
ii. Number of leads in vascular space	LOW	MODERATE	HIGH

iii. Type of lead	LOW	MODERATE	HIGH
iv. BMI of patient	LOW	MODERATE	HIGH
v. Patient age	LOW	MODERATE	HIGH
vi. Gender (male=1 point, female=2 points)			

TOTAL: 6-8 points = overall LOW risk , 9-11 = MODERATE risk, 12-17 = HIGH risk

- b. Are you planning on inserting the Philips Rescue Balloon guidewire (PRB-G) during this case?
  - i. If Yes, why?
  - ii. If No, why not?
  - iii. If you are going to use the PRB-G, are you planning on inserting the Rescue Balloon up front? YES or NO

Two or more large (7F – 12F) venous sheaths will be inserted in the right and left femoral veins as per standard of care as part of the TLE procedure. A 8.5F SRO or other long sheath can help direct the IVUS (Visions® PV.035) catheter and may be used as one of the two standard of care access sheaths. If a long sheath is not used, an 8.5 F short sheath is the minimum size required to use the IVUS catheter.

Prior to pocket access, the IVUS catheter is inserted through a right or left femoral venous approach and advanced under fluoroscopic guidance to the RA. If the pacemaker lead entry is in left pectoral region, imaging will begin from the innominate vein using the medial end of left clavicle as the origin, registered under fluoroscopy. If the pacemaker leads start from right pectoral region, then imaging begins in the cranial portion of SVC, using the medial end of the right clavicle as origin, registered under fluoroscopy. A 0.32 guidewire can help with IVUS catheter manipulation if necessary.

Based on fluoroscopy alone, in left sided device implants, the chest will be divided into 3 zones: Zone 1 includes the area between the head of the clavicle and the innominate vein; zone 2 includes the area between the innominate vein to SVC-RA junction and zone 3 includes the area between the SVC-RA junction through to the mid RA. In right sided device implants, zone 1 includes the area between the head of clavicle to the SVC-RA junction; zone 2 includes SVC-RA junction through to the mid RA.

From there the physician retracts the IVUS catheter through the SVC to the RA in a “survey” run, looking for areas of ILA between the lead and the SVC wall in the previously outlined zones. He/she will also note the presence of lead-on-lead binding. At least one representative image from each zone will be recorded, labelled and saved on the IVUS console. Fluoroscopic images of IVUS catheter position at each site of image recording will be saved and labelled. Using the following scale, grading of ILA in each zone of interest, based on relative motion of lead will be performed:

- i. Grade 1: Freely mobile, Rarely adjacent to vasculature
- ii. Grade 2: Restricted mobility, Frequently adjacent to vasculature
- iii. Grade 3: Immobile, Always adjacent to vasculature
- iv. Grade L, added to number: Lead-to-lead binding

If no ILA is seen, the extraction procedure commences.

If physician identifies locations of adhesions, he/she returns the IVUS catheter to those locations to evaluate severity of adhesion and quantify adhesions based on standardized grading scale which is outlined above. Once all adhesions are evaluated, the extraction procedure commences and the physician gains pocket access and prepares the lead for extraction. The subjective amount (small, moderate, large) of pocket calcification needs to be noted.

The physician begins the extraction until the leads are free through the subclavicular space. At this point, a second run of IVUS imaging is done focusing on areas of highest adhesion seen in the initial imaging. These IVUS images will be collected and saved. When adhesion areas are located, traction is applied to lead of interest to watch the dynamic response of lead movement, then regraded accordingly. Both grades, initial and secondary, should be recorded. The highest grade of adhesion seen in the zone of interest is recorded for that lead. Once this is done, the IVUS catheter may or may not be removed during the extraction procedure. It may left in the low RA to monitor for pericardial effusion development. Added imaging protocol should add 10 minutes to the overall procedure.

During the extraction, the following information needs to be recorded: Laser pulse number of lasing per zone, number of handle pulls for mechanical sheath and time of progression through zone of interest.

Once the extraction is completed, the following data will be collected:

Procedural Data to Record:

1. Length of Procedure (Patient-on-table to wheel-out)
2. Order of leads extracted
3. IVUS Procedure
  - a. Length of imaging time
  - b. Location of adhesions (images will be captured and collected for the study)
  - c. Grading of adhesion in zone of interest, based on relative motion of lead:
    - i. Grade 1: Freely mobile, Rarely adjacent to vasculature
    - ii. Grade 2: Restricted mobility, Frequently adjacent to vasculature
    - iii. Grade 3: Immobile, Always adjacent to vasculature
    - iv. Grade L, added to number: Lead-to-lead binding
4. Length of Extraction (Opening pocket to start of re-implantation, if applicable)
5. Extraction tools
  - a. Laser, Mechanical, Dilating Sheath
  - b. Starting sheath size
  - c. Change of sheath size, settings (40 v. 80Hz), and type
  - d. Use of Outer Sheath
  - e. Switching of leads to extract
6. Location of adhesions felt by extractor
7. Operator rating about ease of sheath advancement in each zone (zones 1-3):
  - a. None – removed without sheaths
  - b. 0 – advanced without power assistance
  - c. 1 – Power assistance but easily advanced
  - d. 2 – Power assistance with effort

8. Laser pulse number of lasing per segment
9. Number of handle pulls for mechanical sheath
10. Time of progression through zone of interest
11. Pocket calcification (Y/N)
12. Clinical Outcome Data:
  - a. Extraction procedural success, as defined above
  - b. Major/minor complications, as defined by 2017 HRS consensus guidelines
  - c. Complications from IVUS catheters (if any)

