## OBJECTIVES

We hypothesize that:

IVUS imaging will provide incremental value beyond clinical factors in identifying vascular adherence

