## **SUBJECT SELECTION AND WITHDRAWAL**

### SITES:

Subjects selected for study will be recruited from 4 sites: University of Chicago Medicine, Chicago, IL; Penn Medicine, Philadelphia, PA; University of Michigan, Ann Arbor, MI; Allina Health, St.Paul, MN

Eligibility: Patients that have been recommended for lead extraction are eligible for enrollment.

A total of 100 eligible patients will be enrolled in the study. Twenty-five patients will be enrolled at each site which will allow 2 things: (1) the operator will first become comfortable with interpreting the images obtained from IVUS (5 patients) and (2) imaging from the remaining 20 patients will help reinforce understanding of the grading scale [25 patients x 4 sites = 100 patients]. Assuming a Pearson correlation sample size calculation:

- Power: 80%
- Alpha Value: 5%
- Baseline  $H_0$  Correlation: 0.50
- Alternative Correlation: 0.70
- Drop-Out Rate: 20%
- Sample Size Calculation: 100 patients

See Appendix D for further information.

Inclusion:

- Patients at least 21 years of age
- Patients with at least one lead over 1 year dwell time requiring extraction

Exclusion:

- Inability of patient capacity to provide consent for themselves either due to medical or psychiatric comorbidity
- Venous occlusion to the extent that the IVUS catheter cannot pass
- Leads < 1 year dwell time requiring extraction

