#### Summary Statements

A sample size of 80 achieves 80% power to detect a difference of -0.20000 between the null hypothesis correlation of 0.50000 and the alternative hypothesis correlation of 0.70000 using a two-sided hypothesis test with a significance level of 0.05000.

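### No clinical comparator is named for the incremental-value hypothesis, and the only one the protocol builds, a coarse operator score, would let IVUS take credit for lead age and lead type

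*Combined protocol and SAP*

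**What the plan says.** The Objectives section states a single hypothesis: "IVUS imaging will provide incremental value beyond clinical factors in identifying vascular adherence". Aim 3 promises a systematic assessment of incremental value in finding patients at low risk of a tear in the SVC-RA region. Neither place says which clinical factors form the baseline, in what form, or in what model.

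The Statistical Plan and Considerations section lists Spearman correlations of ILA grade with time and laser pulses per vascular segment, t-tests, and Fisher's exact or chi-square tests. None is adjusted for anything.

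Clinical information is collected in two forms:

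- **Operator form** (Procedure, pre-procedure assessment, item 1a). It asks "Based on the following clinical variables, what is your assessment of risk or difficulty of extraction". Dwell time, number of leads, type of lead, BMI and age are each rated 1 to 3 by judgement. Gender scores 1 or 2 by rule. The total is banded 6–8, 9–11 and 12–17.
- **Recorded values** (Screening Visit). These include "Lead dwell times", lead type with SVC coil, number of leads, age, gender and BMI. No analysis uses them.

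IVUS is graded in each zone, and the second-run instruction adds: "The highest grade of adhesion seen in the zone of interest is recorded for that lead". Laser pulses and progression time are recorded by zone.

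**The concern.** Background and Rationale names longer dwell time, a high-voltage coil, multiple leads, female gender, low BMI and younger age as associated with ILA. By the protocol's own account, then, these factors can drive the IVUS grade and, through adhesion, the difficulty of extraction. An incremental-value claim has to remove their contribution first.

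The unadjusted correlations do not attempt this. If an incremental analysis is added later, the operator form is the obvious ready-made baseline, because it is the only assessment explicitly based on clinical variables alone. But a three-step opinion without cut-offs is a blurred copy of dwell time and lead type. In a patient whose leads differ in age or type, one line cannot describe both. Whatever the score loses, the IVUS grade can pick up. The hypothesis could then be declared confirmed although IVUS adds nothing to what the chart already holds.

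**Working it through.** **1. The plan's own figure.** Inputs from Appendix D and the sample-size list under Sites: "using a two-sided hypothesis test with a significance level of 0.05000"; "null hypothesis correlation of 0.50000"; "Alternative Correlation: 0.70"; "Drop-Out Rate: 20" per cent.

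- Exact distribution of the sample correlation: power 0.80092 at N = 80, matching Appendix D (0.7958 at N = 79).
- Fisher-z check: n = ((1.960 + 0.842)/(0.8673 − 0.5493))² + 3 = 80.6, so 81.
- Enrolment: 80/(1 − 0.20) = 100.

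The figure reproduces. It is for an unadjusted correlation and gives no power for an incremental test.

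**2. The score.** Minimum 5×1 + 1 = 6; maximum 5×3 + 2 = 17. Of 3⁵×2 = 486 answer patterns, 27 fall in the low band, 216 in the moderate and 243 in the high. The bands cover the range without gaps, so the arithmetic of the form is sound. The issue is the information it discards.

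**3. Levels.**

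| Item | Level at which it is recorded |
|---|---|
| Operator score | Once per case (implied by the form) |
| IVUS grade | Zone, with the highest grade attributed to a lead |
| Laser pulses, progression time | Zone; not stated to be per lead |
| Dwell time, lead type, SVC coil | Listed under Lead Data |

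**4. Simulation.** No closed formula applies. All distributions, effect sizes and cut-offs below are assumptions. In each set, IVUS grade and difficulty depend on the same clinical values with independent errors, so the true increment is zero. The IVUS term is tested at 5% by least squares with patient-clustered standard errors, in 80 patients.

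*Set A* (500 runs per cell). Two leads per patient, within-patient dwell-time correlation 0.5–0.8, clinical factors correlating 0.4–0.6 with both difficulty and latent grade. Share of runs in which IVUS tests as incremental:

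| Comparator | Two leads | One lead |
|---|---|---|
| Score total | 20–82% | 8–34% |
| Score band | 25–88% | 10–47% |

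With identical cut-offs for all operators, the two-lead rate over the total is still 16–72%. With recorded lead-level values as comparator the rate is 3–7%.

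*Set B* (1,000 runs per cell). Lead dwell time, coil and zone drive both variables. IVUS noise SD is 1, 2 or 4, giving raw Spearman correlations with difficulty of about 0.51, 0.33 and 0.18 in the lead-zone analysis.

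| Analysis | Over banded score | Over recorded values |
|---|---|---|
| Lead-zone, 1–3 leads | 100%, 100%, 89% | 6.1%, 4.8%, 6.1% |
| All single-lead | 100%, 96%, 54% | 6.4%, 4.9%, 5.6% |
| Worst grade per patient | 99%, 71%, 29% | 7%, 10%, 13% (patient-level summaries) |

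In the lead-zone analysis the spurious gain in R² over the banded score is 0.19, 0.08 and 0.025, against about 0.001 over the recorded values. Using the 6–17 total instead of bands gives 100%, 100% and 88%.

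Monte Carlo error at a true 5% is √(0.05×0.95/1000) = 0.7 points, so the single-lead and lead-zone rates over recorded values are close to nominal. The 10% and 13% patient-level rates are above it.

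**5. Which feature causes it.** Set A's one-lead rates are lower partly because observations fall from 160 to 80. With 160 single-lead observations, where no level mismatch exists, the rates are 11–50% (total) and 16–69% (band). Giving the operator score separately for each lead yields 12–46% and 15–66%. The same recheck with one score per two-lead patient gives 17–74% and 25–86%. Coarseness alone therefore produces much of the effect, and the patient-level unit adds to it.

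**The case against.** **The score is not designated as the comparator.** This stands. A reader might infer that the operator score is what IVUS must beat, but no section says so. An analyst could use the recorded screening values without contradicting any text. The firm finding is that the comparator is unspecified; the bias follows only if the score fills the gap.

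**Aim 3 is a patient-level target.** This also stands. A reader might infer that a patient-level score is at the wrong level throughout. For Aim 3 it is not. Matching the level does not cure coarseness, however: with the patient's worst grade, set B still gives 29–99% over the banded score, and a recheck under set A's assumptions gives 12–42% (total) and 15–60% (band).

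**The simulated outcome is difficulty, not adherence or tear.** True. Difficulty is the Aim 2 outcome. Adherence itself is graded by IVUS, so difficulty serves as the outside yardstick. The plan should say so.

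**The benchmark is favourable.** It is. The recorded-value model contains the variables that generated the data; a real model may be misspecified and do less well.

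**Operator judgement is a legitimate comparator.** Whether IVUS changes the picture relative to the operator's view is a fair descriptive question. It is not the question of value beyond clinical factors.

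**Conclusion.** The point holds as a gap in specification with a foreseeable bad default. The plan states an incremental-value hypothesis, names no comparator, plans only unadjusted tests, and builds one clinical-only measure that is too coarse for the purpose. As written, it cannot separate what IVUS adds from what lead age and type already tell.

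If the score is used, the simulations give false increments well above 5%, including in single-lead patients. The spread, from 8% to 100% at lead or zone level, reflects the assumptions about lead numbers, correlations and noise, none of which the documents supply. A reader might infer that this trial would report a false increment at some particular rate. That is not supported: the simulations show that the error can occur and can be large, and no more. Nor is it supported that the mismatch between patient and lead is the main cause, since coarseness is enough by itself. No change to the sample size follows from this point.

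**What to change.** In Statistical Plan and Considerations, state that the Objectives hypothesis is tested by adding IVUS grade to a model of extraction difficulty that already contains the recorded screening values: dwell time in years, lead type and SVC coil, number of leads, age, BMI and sex, plus zone. Code zone by anatomy, because zone 2 denotes different segments in left- and right-sided implants. Fit the model at the level at which grade and difficulty are recorded: lead-zone if the case forms link both to a lead, otherwise zone with the lead values summarised. Use patient-clustered standard errors and report the change in fit.

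For Aim 3, use patient-level summaries of the same values, such as longest dwell time and any SVC coil. Set B suggests that these summaries do not fully restore the nominal error rate (7–13%), so word that result cautiously. Report any comparison with the operator score as descriptive only, not as evidence of incremental value.

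The cost is mainly analysis wording, because the clinical values are already collected. The model has several terms instead of one, and the reported increment will probably be smaller. The sponsor must also check whether the forms tie pulses and progression time to individual leads; if they do not, a lead-level analysis would need a change to the forms.

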## **PRIMARY ENDPOINTS**

1. Ability of IVUS to image ILA

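### The primary endpoint has no denominator, success criterion or analysis, and the ILA scale has no entry for an ungradable zone, so the plan has no way to register an imaging failure

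*Combined protocol and SAP*

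**What the plan says.** - **Endpoint.** The section PRIMARY ENDPOINTS contains one item: "Ability of IVUS to image ILA". No unit, denominator, threshold or comparator is given.
- **Analysis.** STATISTICAL PLAN AND CONSIDERATIONS correlates ILA grade with traversal time and laser pulses and names generic tests. It does not analyse imaging success. The sample size (SUBJECT SELECTION AND WITHDRAWAL; Appendix D) is for a correlation, which is listed under SECONDARY ENDPOINTS.
- **Scale.** PROCEDURE asks for "grading of ILA in each zone of interest, based on relative motion of lead". The scale runs from "Grade 1: Freely mobile, Rarely adjacent to vasculature" to "Grade 3: Immobile, Always adjacent to vasculature", plus an L suffix for lead-to-lead binding. The same codes recur in the list of procedural data.
- **Branch.** After the survey run, "If no ILA is seen, the extraction procedure commences". Where adhesions are identified, the operator goes back for a targeted look. The first branch has no grade tied to it.
- **Images.** "At least one representative image from each zone will be recorded, labelled and saved on the IVUS console", with a fluoroscopic image of the catheter position at each recording site.
- **Eligibility.** Patients with venous occlusion that stops the catheter are excluded. A venogram before extraction is at the operator's discretion.
- **Possible comparator.** "Location of adhesions felt by extractor" is collected but not linked to the primary endpoint.

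**The concern.** An endpoint about the ability to image needs a place to record inability, and the plan has none. A zone without an entry could have been clean, unreadable, or not applicable, since right-sided implants have two zones and left-sided ones three. The protocol does draw this kind of line elsewhere: the rating of sheath advancement separates removal without a sheath from its lowest grade.

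Two things are at stake. First, the primary result could look perfect because failures have nowhere to go. Second, unreadable zones filed at the bottom of the scale would contaminate the low end of the correlation between grade and difficulty. They would also contaminate the group that Aim 3 wants to identify as low risk. Failures are plausible: the protocol sets aside 5 patients per site (20 of 100) for operators to get used to reading the images.

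**Working it through.** **1. The plan's own figure.** Inputs from Appendix D: null correlation 0.50, alternative 0.70, two-sided alpha 0.05, power 80%, dropout 20%. By Fisher's z, n = ((1.960 + 0.842)/(atanh 0.70 - atanh 0.50))² + 3 = 80.6. Power at 80 is 0.797, or 0.800 with bias correction, against a stated 0.80092. Inflation gives 80/(1 - 0.20) = 100. The figure reproduces, but it serves the secondary correlation. The documents give no figure for the primary endpoint.

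**2. What the scale can record.**

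| What happened | Entry available under the plan |
|---|---|
| Lead seen, restricted or immobile | Grade 2 or 3 |
| Lead seen, not adherent | Grade 1 on the natural reading; blank if the no-ILA branch is taken to end recording |
| Lead not seen or image unreadable | None: blank, or a guessed grade |
| Zone 3 in a right-sided implant | None: blank |
| Catheter cannot pass | Patient excluded |

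The last four rows can all leave no grade.

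**3. Possible contamination.** Let f be the share of zones not visualised (assumed 5-20%) and p the true share of zones with ILA (assumed 30-70%). Suppose that failures are independent of ILA and are all filed as no ILA. Then

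- apparent ILA share = p(1 - f);
- share of apparent no-ILA zones that are failures = f/(f + (1 - f)(1 - p)).

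| f | Apparent ILA share, p = 50% | Failures among no-ILA zones, p = 50% | Same, p = 30% to 70% |
|---|---|---|---|
| 0% | 50% | 0% | 0% |
| 5% | 47.5% | 9.5% | 7.0% to 14.9% |
| 10% | 45% | 18.2% | 13.7% to 27.0% |
| 20% | 40% | 33.3% | 26.3% to 45.5% |

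For example, at f = 10% and p = 50%: 0.10/(0.10 + 0.90 × 0.50) = 0.10/0.55 = 18.2%.

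**4. Precision of a defined endpoint.** Exact binomial 95% intervals for the proportion of patients successfully imaged:

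| Success | N = 100 | N = 80 |
|---|---|---|
| 100% | 96.4-100% | 95.5-100% |
| 95% | 88.7-98.4% | 87.7-98.6% |
| 90% | 82.4-95.1% | 81.2-95.6% |
| 80% | 70.8-87.3% | 69.6-88.1% |

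**5. Zones are not patients.** If 10% of zones are ungradable, independently and with one lead per patient (assumed), the share of patients with every zone gradable is 0.9³ = 72.9% for three zones and 0.9² = 81% for two, not 90%. The unit must therefore be stated.

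**The case against.** A reader might infer that the scale has no place for a zone that was imaged and showed no ILA. The documents do not support that. The instruction to grade each zone comes before the no-ILA sentence, and a freely mobile lead rarely next to the wall is a natural description of a non-adherent one. Read in order, the branch skips only the targeted second look. What stands is narrower: the text never says that no ILA means Grade 1, so sites may differ.

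A reader might also infer that failure and absence are indistinguishable, so that the endpoint is bound to be biased. That is too strong. If every zone is graded, a clean zone is a 1 and a blank is different. A missing or poor zone image could also reveal a failure later. But no rule assigns such a review, and the scale rests on relative motion, while the plan does not say that the saved images capture motion. Recovery is therefore partial and unplanned.

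Finally, the case report form is not among the documents and may have a not-assessed field. If so, the protocol still does not say how that field enters the primary endpoint.

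**Conclusion.** The point holds in this form: followed as written, the plan yields no primary result that can show an imaging failure. The undefined endpoint is the basic defect. The missing not-gradable entry matters because a failure is best captured at the procedure. The exclusion of patients in whom the catheter cannot pass adds to the problem, since some of these may be found only on attempt and then drop out of the count.

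The size of any bias cannot be derived from the documents. It is zero if no zone fails. Under the assumed ranges above, and only if failures are filed as no ILA, 7.0% to 45.5% of apparent no-ILA zones would be failures at failure rates of 5-20%. The stated sample size of 80 evaluable and 100 enrolled is unaffected.

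**What to change.** 1. State that Grade 1 includes a lead that was seen with no ILA. Require a grade for every applicable zone and lead, including when no ILA is seen. Do not add a Grade 0: nothing would separate it from Grade 1, and it would blur the scale used in the correlation.
2. Add one code, not visualised/not gradable, with the reason.
3. Define the primary endpoint as the proportion of patients with IVUS attempted who have every applicable zone gradable, with an exact 95% CI (for example 95/100: 88.7-98.4%; 76/80: 87.7-98.6%). Count in the denominator patients in whom the catheter proves unable to pass at the procedure, and align the exclusion criterion with this. A per-patient unit also avoids treating zones within a patient as independent.
4. Leave not-gradable zones out of the grade correlation and report how many there were.
5. A gradable zone does not show that ILA was correctly imaged. As supportive evidence, cross-tabulate IVUS grade by zone against the adhesions felt by the extractor, which are already collected. This is supportive only, because nothing in the plan blinds the extractor to the IVUS grades.

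The cost is one more code, a few sentences in the protocol, and a success rate that may look less favourable.
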